7.1.3. Overview of Planned PK Dose Escalation Analyses

Dose escalation for the first 2 dose levels will be based on population PK modelling (if feasible) or on the assumption of dose–exposure proportionality (i.e., doubling the dose gives an approximate doubling of exposure). If prior PK results show less than proportional increase in exposure with increasing dose, the prediction will be based on the assumption that the fold exposure increase to fold dose increase ratio will be the same with the current dose escalation as it was with the previous one. If prior PK results show more than proportional increase in exposure with dose, subsequent dose escalations will not be higher than 3-fold.

The population PK model will be a fit for purpose model. Candidate model selection will be primarily based on a significant reduction in the objective function value (≥ 3.32 , $\chi^2 < 0.05$) and improvement in the fits of diagnostic scatter plots. Inter-individual variability will be modelled using an exponential error model and residual error will be described by a proportional, proportional plus additive, or additive error model, depending on the data. Model performance will be evaluated using a visual predictive check. Simulations for dose recommendations will be conducted to determine the probability of an individual subject exceeding the defined exposure margins for AUC and Cmax.

7.2. Final Analyses**7.2.1. Pharmacokinetic Analyses**

The reconciliation of the PK Case Report Form (CRF) and will be performed by, or under the direct auspices of, Clinical Pharmacology Science and Study Operations (CPSSO), GlaxoSmithKline.

The merge of PK concentration data, randomisation and CRF data will be performed by, or under the direct auspices of QSI, GlaxoSmithKline.

Derivation of pharmacokinetic parameters will be performed by or under the direct auspices of CPMS, QSci, GlaxoSmithKline.

Statistical Analysis of pharmacokinetic parameters will be performed by or under the direct auspices of, QSI, GlaxoSmithKline.

7.2.1.1. Overview of Planned Pharmacokinetic Analyses

The pharmacokinetic (PK) analyses will be based on the “Pharmacokinetic” population, unless otherwise specified.

Table 4 provides an overview of the planned non-compartmental pharmacokinetic analyses, with full details being presented in [Appendix 10: List of Data Displays](#).

Table 4 Overview of Planned Pharmacokinetic Analyses

Display Type	Untransformed						Log-Transformed						
	Stats Analysis			Summary		Individual	Stats Analysis			Summary		Individual	
	T	F	L	T	F	F	L	T	F	L	T	F	F
Descriptive statistics													
Plasma Drug Concentrations				Y	Y	Y	Y				Y		
PK Urine Concentrations				Y	Y	Y	Y						
Derived PK Parameters				Y	Y		Y				Y		
PK Urine Parameters							Y						
Statistical Analysis of Primary PK Parameters													
Dose Proportionality								Y		Y[1]			
Food Effect								Y		Y[1]			
Time Invariance of GSK3036656								Y		Y[1]			
Accumulation ratio								Y		Y[1]			
Achievement of Steady State								Y		Y[1]			

NOTES :

- T = Table, F = Figure, L = Listings, Y = Display generated.
- Stats Analysis = Represents TFL related to any formal statistical analyses (i.e. modelling) conducted.
- Summary = Represents TFL related to any summaries (i.e. descriptive statistics) of the observed raw data.
- Individual = Represents FL related to any displays of individual subject observed raw data.

1. Supportive SAS Output from Statistical Analysis

7.2.1.2. Drug Concentration Measures

Refer to [Appendix 4: Data Display Standards & Handling Conventions \(Section 10.4.3. Reporting Process & Standards\)](#).

7.2.1.3. Pharmacokinetic Parameters

7.2.1.3.1. Deriving Pharmacokinetic Parameters

- Refer to [Appendix 4](#): Data Display Standards & Handling Conventions (Section 10.4.3. Reporting Process & Standards).
- Plasma GSK3036656 concentration-time data will be analyzed by non-compartmental methods according to current working practices with WinNonlin 5.2 or higher.
- Non-compartmental analysis will be performed in accordance with GSK PK Guidance document GUI_51487.
- All calculations of non-compartmental parameters will be based on actual sampling times recorded during the study.
- Pharmacokinetic parameters described in [Table 5](#) will be determined from plasma concentration-time data and urine concentration data, as data permits.

Table 5 Derived Pharmacokinetic Parameters

Parameter	Parameter Description
AUC(0-t)	Area under the concentration-time curve from time zero to the time of the last quantifiable concentration (C(t)) will be calculated using the linear trapezoidal rule for each incremental trapezoid and the log trapezoidal rule for each decremental trapezoid.
AUC(0-∞)	Area under the concentration-time curve extrapolated to infinity calculated as: $\text{AUC} = \text{AUC}(0-t) + C(t) / \lambda_z$
AUC(0-24h)	Area under the concentration-time curve from time zero to 24 hours post-dose
AUC(0-τ)	AUC from time zero during a dosing interval of duration “τ”
AUC(Ro)	Observed accumulation ratio (Ro) for AUC will be calculated as follows: $\text{Day 14 AUC}(0-\tau) / \text{Day 1 AUC}(0-\tau)$
Ae	Urinary excretion of unchanged drug
Cmax	Maximum observed blood concentration, determined directly from the concentration-time data.

Parameter	Parameter Description
Ctrough	Pre-dose observed concentration, will be obtained directly from the concentration-time data.
CLr	Renal clearance
Fe	Fraction of the dose excreted in the urine
Lambda_z	The first order rate constant associated with the terminal (log-linear) portion of the concentration-time curve.
Rss	Steady state ratio (Rss) will be calculated as follows: Day 14 AUC(0- τ)/Day 1 AUC(0- ∞)
RCmax	Observed accumulation ratio for Cmax (RCmax) will be calculated as follows: Day 14 Cmax/Day 1 Cmax
tmax	Time to reach Cmax, determined directly from the concentration-time data.
t _{1/2}	Apparent terminal phase half-life will be calculated as: $t_{1/2} = \ln 2 / \text{Lambda}_z$ (NOTE: Lambda_z is the terminal phase rate constant).

7.2.1.3.2. Statistical Analysis of Pharmacokinetic Parameters

For each of the parameters AUC (AUC(0- ∞), AUC (0- t), AUC(0- τ), AUC(Ro)), RCmax, Rss, Ct, Ae, fe, CLr and Cmax the following summary statistics will be calculated and tabulated by dose group for study Part A and Part B separately:

- **Untransformed Data:** N, n, arithmetic mean, 95% confidence interval (CI) for the arithmetic mean, SD, median, minimum, maximum.
- **Log_e-transformed Data:** Geometric mean, 95% CI for the geometric mean, SD of log_e-transformed data and %CVb.

For tmax, and t_{1/2} the summary statistics specified for untransformed data above will be generated.

The following pharmacokinetic statistical analyses will only be performed, if sufficient data is available (i.e. if subjects have well defined plasma profiles). Pharmacokinetic analysis will be the responsibility of the Clinical Pharmacology Modeling and Simulation Department, (CPMS) and Statistical analyses of the pharmacokinetic parameter data will be the responsibility of QSI Stats & Programming.

Pharmacokinetic Statistical Analyses (Dose Proportionality - Single and Repeat Dose Study Phases)	
Endpoint(s)	

 • Single Dose: AUC(0-t), AUC(0-∞) and Cmax • Repeat Dose : AUC(0-τ) and Cmax 	
Model Specification	

 • Will be statistically analysed using the power model • $y = \alpha^* \text{dose}^\beta$ 
Where y =PK parameter being analyzed and α= subject
 
 • Log_e transformed data will be analysed by fitting the following terms in the mixed effect model: 
 • Fixed effect: log_e (dose) • Random effect: Subject 	
Model Checking & Diagnostics	

 • Refer to Appendix 8: Model Checking and Diagnostics for Statistical Analyses. 	
Model Results Presentation	
Estimates of the mean slopes of log _e (dose) will be reported along with corresponding 90% confidence intervals (slope≈1 implies dose proportionality).	

Pharmacokinetic Statistical Analyses (Food Effect - Single Dose Study Phase)	
Endpoint(s)	

 • AUC(0-t), AUC(0-∞), Cmax and t_{1/2} 	
Model Specification	

 • Will be statistically analysed using a mixed model (MM). • Terms fitted in the mixed effect ANOVA model will include: 
 • Fixed effect : fed/fasted • Random Effect : Subject • Only data from the same dose level as the fed dose group will be included in this analysis, all other dose level data will be excluded. • The Kenward and Roger method for approximating the denominator degrees of freedom and correcting for bias in the estimated variance-covariance of the fixed effects will be used. • An unstructured covariance structure for the G matrix will be used. 
 ◦ In the event that this model fails to converge, alternative covariance structures may be considered such as VC or CS. ◦ Akaike's Information Criteria (AIC) will be used to assist with the selection of covariance structure. 	
Model Checking & Diagnostics	

 • Refer to Appendix 8: Model Checking and Diagnostics for Statistical Analyses. 	

Pharmacokinetic Statistical Analyses (Food Effect - Single Dose Study Phase)	
Model Results Presentation	
Point estimates and corresponding 90% confidence intervals will be constructed for the comparisons of interest of GSK3036656 fed – GSK3036656 fasted, using the residual variance. These will then be back-transformed to provide point estimates and corresponding 90% confidence intervals for the geometric mean ratios fed:fasted.	
Endpoint(s)	

 • Tmax 	
Model Specification	

 • Wilcoxon matched pair test • Only data from the same dose level as the fed dose group will be included in this analysis, all other dose level data will be excluded. 	
Model Checking & Diagnostics	

 • Refer to Appendix 8: Model Checking and Diagnostics for Statistical Analyses. 	
Model Results Presentation	
Point estimate and 90% confidence interval for the median difference (fed – fasted)	

Pharmacokinetic Statistical Analyses (Time Invariance of GSK3036656 - Repeat Dose Study Phase)	
Endpoint(s)	

 • time invariance ratio 	
Model Specification	

 • Will be statistically analysed using a mixed model (MM) ANOVA. • Fixed, categorical effect : day • Random Effect : Subject 
AUC(0-inf) on Day 1 will be the reference phase in the analysis, while AUC(0- τ) on Day 14 will be the test phase, using log-transformed AUC.
	

 • The Kenward and Roger method for approximating the denominator degrees of freedom and correcting for bias in the estimated variance-covariance of the fixed effects will be used. • An unstructured covariance structure for the G matrix will be used. 
 ◦ In the event that this model fails to converge, alternative covariance structures may be considered such as VC or CS. ◦ Akaike's Information Criteria (AIC) will be used to assist with the selection of covariance structure. 	
Model Checking & Diagnostics	

 • Refer to Appendix 8: Model Checking and Diagnostics for Statistical Analyses. 	
Model Results Presentation	

 • The time invariance ratio of GSK3036656 will be estimated by calculating the ratio of the generalized least square means of AUC (0- τ) on Day 14 to AUC (0-inf) on 	

Pharmacokinetic Statistical Analyses (Time Invariance of GSK3036656 - Repeat Dose Study Phase)

Day 1, along with the corresponding 90% CI at each dose level.
--

Pharmacokinetic Statistical Analyses (Accumulation - Repeat Dose Study Phase)
--

Endpoint(s)

• AUC (Ro) and Cmax (RCmax)

Model Specification

 Will be statistically analysed using a mixed model (MM) using a log_e-transformation. Fixed effects : dose, day and dose*day Random Effect : Subject

 The Kenward and Roger method for approximating the denominator degrees of freedom and correcting for bias in the estimated variance-covariance of the fixed effects will be used. An unstructured covariance structure for the G matrix will be used. 
 In the event that this model fails to converge, alternative covariance structures may be considered such as VC or CS. Akaike's Information Criteria (AIC) will be used to assist with the selection of covariance structure.

Model Checking & Diagnostics

• Refer to Appendix 8 : Model Checking and Diagnostics for Statistical Analyses.
--

Model Results Presentation


 Point estimates and 90% confidence intervals for the differences “Day 14- Day 1” will be constructed using the appropriate error term. The point estimates and associated 90% confidence intervals will then be exponentially back-transformed to provide point and 90% confidence interval estimates for the ratios “Day 14: Day 1” for each active dose. If both the dose and day by dose interaction terms are not significant, a single point estimate and confidence interval pooled across all doses will also be constructed.
--

Pharmacokinetic Statistical Analyses (Achievement of Steady State - Repeat Dose Study Phase)

Endpoint(s)

• Trough plasma concentrations at the end of the dosing interval (C _T)
--

Model Specification

 Will be statistically analysed using a mixed models (MM) using log-transformed dose data. Fixed effects : dose, day and dose*day Random Effect : Subject

 The Kenward and Roger method for approximating the denominator degrees of freedom and correcting for bias in the estimated variance-covariance of the fixed

Pharmacokinetic Statistical Analyses (Achievement of Steady State - Repeat Dose Study Phase)

effects will be used.

- An unstructured covariance structure for the G matrix will be used.
 - In the event that this model fails to converge, alternative covariance structures may be considered such as VC or CS.
 - Akaike's Information Criteria (AIC) will be used to assist with the selection of covariance structure.

Model Checking & Diagnostics

- Refer to [Appendix 8: Model Checking and Diagnostics for Statistical Analyses](#).

Model Results Presentation

The coefficients of the slopes for the day effect for each dose, along with corresponding 90% confidence intervals, will be used to determine whether steady state was achieved. If the day-by-dose interaction were not significant, then the point estimates and 95% CIs for the individual dose levels will also be pooled across all doses for a single D14/D1 ratio.

Trough concentration levels collected pre-morning dose will be plotted by collection day and dose.

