4. STUDY DESIGN

4.1. Part A (Single Dose)

Figure 1 Part A Schematic

★ Dose escalation meeting

- o One of the dosing periods will be a food effect group – the dose will be determined based on data from previous cohorts
- o There will be a 2 week washout between doses initially but the washout period may be modified depending on emerging data from previous cohorts.
- o Cohorts 1 and 2 will be dosed sequentially. If it is considered desirable to dose Cohorts 1 and 2 in an overlapping/interlocking fashion, approval will be sought from the Regulatory Agency first.

Up to two cohorts will be included in the single dose part (Part A). Each cohort will participate in up to 4 treatment (dosing) periods (including a food effect treatment period). Initially, there will be a 14 day wash out period for individual subjects between each dose level which is considered sufficient in light of the predicted half-life of GSK3036656 [on average, approximately 30 hours (range: 12 to 72 hours) based on the various preclinical extrapolation methods], however this may be revised once relevant PK data is obtained. Nine subjects per cohort will be enrolled and randomised to ensure adequate safety, tolerability and PK information is gained and a balanced randomisation is achieved across all treatment (dosing) periods.

During each treatment (dosing) period, GSK3036656 will be administered to 6 subjects and placebo will be administered to 3 subjects. As this is a FTIH study, each treatment (dosing) period will be staggered over 2 days. On Day 1 of each dose level, one subject will receive GSK3036656 and one subject will receive placebo. The remaining subjects within the dosing group will be dosed one day later provided satisfactory safety and tolerability is demonstrated for the subjects dosed on Day 1. A treatment (dosing) period does not have to be staggered if the dose administered is equal to or lower than a dose that has been already tested and found to be safe and well tolerated.

Subjects will attend the unit on Day -1 for assessments and a meal. The subjects will then fast overnight (at least 8 hours) and be dosed the following morning (Day 1). Dosing with food may also be done in Part A once results from the food effect analysis are available. Dividing the total dose for the treatment (dosing) period into 2 or 3 smaller doses administered within 24 hours may also be done. The decision to divide the total dose into

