A statistical analysis will be performed using the power model. The analysis will be performed on \log_e -transformed data. For each of these parameters a mixed effects model will be fitted with \log_e (dose) as a fixed effect and individual subject fitted as random effects. Estimates of the mean slopes of \log_e (dose) will be reported along with corresponding 90% confidence intervals (slope ≈ 1 implies dose proportionality).

Food Effect (Single Dose Study)

The effect of food on the pharmacokinetics of GSK3036656 will be examined. AUC(0-t), AUC(0- ∞), Cmax, and $t_{1/2}$ of GSK3036656 will be analysed after a \log_e -transformation of the data. An analysis of variance model will be fitted along with 90% confidence intervals using a mixed effects model, with fed/fasted condition as a fixed effect and subject as a random effect. Point estimates and corresponding 90% confidence intervals will be constructed for the comparisons of interest of GSK3036656 fed – GSK3036656 fasted, using the residual variance. These will then be back-transformed to provide point estimates and corresponding 90% confidence intervals for the geometric mean ratios fed:fasted.

Tmax will be analyzed non-parametrically using a Wilcoxon matched pairs test to compute the point estimate and 90% confidence interval for the median difference (fed – fasted).

Accumulation (Repeat Dose Study Phase)

The extent of accumulation of GSK3036656 will be based on AUC (Ro) and Cmax (RCmax).

The focus of the statistical analysis will be to estimate the accumulation ratio, Ro, on the pharmacokinetics of GSK3036656. Following \log_e -transformation, AUC(0- τ) on Day 14 and AUC(0- τ) on Day 1 will be analysed by a mixed effect model, fitting fixed effect terms for dose, day, and day by dose interaction, and fitting subject as a random effect. For each dose, point estimates and 90% confidence intervals for the differences “Day 14- Day 1” will be constructed using the appropriate error term. The point estimates and associated 90% confidence intervals will then be exponentially back-transformed to provide point and 90% confidence interval estimates for the ratios “Day 14: Day 1” for each active dose. If both the dose and day by dose interaction terms are not significant, a single point estimate and confidence interval pooled across all doses will also be constructed.

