4. ANALYSIS POPULATIONS

Population	Definition / Criteria	Endpoint(s) Evaluated
Enrolled Population	
 Defined as all subjects who were enrolled for the trial irrespective of whether they were randomized or not and for whom a record exists on the study database. 	
 Screen Failure
Safety Population	
 Defined as all randomised subjects who receive at least one dose of study medication. If subjects receive a treatment different to their randomised treatment, they will be analysed according to the treatment actually received. 	
 Study Population Safety
Pharmacokinetic (PK) Population	
 Subjects in the Safety population who administered at least one dose of active treatment and have at least one evaluable PK sample. 	
 PK

NOTES :

- Please refer to [Appendix 10](#) which details the population to be used for each display being generated.

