7.1.1. Overview of Planned Bayesian Dose Escalation Analyses

The Bayesian Dose Escalation analyses will be utilised to guide dose selection after 3 doses in each part of the study. The analyses will be based on the PK population, unless otherwise specified.

During dose escalation, a Bayesian predictive probability of geometric mean $AUC[0-24] > 4.9 \mu\text{g.h/ml}$ and $C_{max} > 0.443 \mu\text{g/ml}$ will be calculated for potential future dose levels and used together with safety and tolerability data to aid next dose selections. The Bayesian predictive probability will be based on Whitehead's method (Whitehead 2001).

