7.1.2. Planned Bayesian Statistical Analyses

Bayesian Statistical Analyses	
Endpoint(s)	
• $AUC[0-24]$	
• C_{max}	
Model Specification	
To guide dose selection after 3 doses in each part of the study have been observed, Bayesian posterior inferences about population probability distributions of model parameters of PK parameters will be assessed by using the following power model:	
$y = \exp(\theta_1 + r_i + \epsilon) \cdot dose^{\theta_2}$	
where y denotes the PK parameter being analyzed and r the random subject effect. The θ_s , $s=1,2$, in the power model will be estimated by linear regression of the \log_e -transformed PK parameters on \log_e dose levels.	
$\log(y_{ij}) = \theta_1 + \theta_2 \cdot \log(d_{ij}) + r_i + \epsilon_{ij} \quad (1)$	
where	

 y_{ij} is the observed or predicted PK variable of the j-th dose d_{ij} administered to the i-th subject. In particular, it is an $AUC[0-24]$ or a C_{max}, as applicable. θ_1, θ_2 are population intercept and slope, respectively. r_i is the random effect associated with subjects, it has mean zero and variance s^2 ϵ_{ij} is a random error term, with mean zero and variance σ^2. 	
Note, for part B, subjects will not receive more than one dose, therefore the random subject effect (r_i) will not be included in that model.	
In general, Bayesian inference seeks to quantify the probability distributions of model parameters such as the $(\theta_1, \theta_2, \sigma, s)$ defined in Equation (1). The present inference will	

Bayesian Statistical Analyses

incorporate a normal prior distribution, to express the prior information about the parameters (θ_1, θ_2) and a gamma prior distribution for (s^2, σ^2). Due to limited information available about the GSK3036656 compound, a non-informative prior with large variance will be used. For ease of parameterization for the normal distribution in computer programming, use $v = \sigma^{-2}$ and $w = s^{-2}$ as the precision. Model parameters are assumed *a priori* to be independent.

Table 3 Prior Distributions

Model Parameter	Prior
θ_1 (intercept)	\sim Normal (0, precision=0.001)*
θ_2 (slope of log-dose)	\sim Normal (0, precision=0.001)*
v (random error precision)	\sim Gamma (0.01, iscale=0.001)*
w (random effect precision)	\sim Gamma (0.01, iscale=0.001)*

All model parameters are *a priori* independent.

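### Part A power models have no food or regimen term and no data restriction, so the planned fed period, and any later fed or divided doses, would be pooled with fasted single doses

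*SAP*

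**What the plan says.** **Final model.** SAP 7.2.1.3.2 (Dose Proportionality) says the parameters "Will be statistically analysed using the power model". It continues "Log_e transformed data will be analysed by fitting the following terms in the mixed effect model" and lists log dose as fixed and subject as random. Protocol 10.3.2.2 specifies the same model. Neither mentions feeding state or dose division.

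**Escalation model.** SAP 7.1.2 regresses the log PK parameter on log dose, with a random subject effect in Part A only. The response "is the observed or predicted PK variable of the j-th dose" given to a subject; the text does not say whether dose means the total or each administration. On the data set, SAP 7.1.1 says: "The analyses will be based on the PK population, unless otherwise specified". SAP 4 defines that population as "Subjects in the Safety population who administered at least one dose of active treatment and have at least one evaluable PK sample".

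**Where a restriction does exist.** The food-effect analysis in SAP 7.2.1.3.2 is limited to the dose level that was also given fed. The power models carry no such rule.

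**What will be dosed.** Protocol 4.1 and 4.1.1 plan one fed period in Part A, at a dose already given fasted in the same cohort. Protocol 4.1 adds two options: "Dosing with food may also be done in Part A once results from the food effect analysis are available", and "Dividing the total dose for the treatment (dosing) period into 2 or 3 smaller doses administered within 24 hours may also be done". Protocol 4.2 has matching options for Part B.

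**Labels.** SAP 10.4.1 lists eight active Part A codes, D1 to D8, all displayed by milligrams only.

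**The concern.** A model whose only covariate is log dose has to put a food effect somewhere. Depending on where the fed dose lies in the dose range, the effect tilts the slope, moves the intercept or enters the residual.

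Two results depend on this. The first is the final proportionality slope and its 90% CI, where a food effect could pass for non-proportional kinetics or hide it. The second is the predicted probability that an individual exceeds 4.9 µg.h/mL for AUC(0-24) or 0.443 µg/mL for Cmax. Protocol 6.3.1 and 6.3.2 accept a proposed dose only if that probability is at most 10%. A prediction below the true value is the unsafe error.

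The timing makes this relevant. Fed dosing may start once two fasted levels are known (Protocol 6.3.1), and the Bayesian model starts after three doses, so fed profiles can form a sizeable share of its first data set.

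**Working it through.** **Plan's own figures.** Protocol 4.5 sets the limits at 1/30 of the dog NOAEL exposures: 147.0/30 = 4.90 and 13.3/30 = 0.443. Both reproduce. The plan states no slope, SD or precision, so nothing else can be reproduced.

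**Inputs from the documents.** Six active subjects per Part A period (Protocol 4.1); 50% CV for clearance (4.5), used here as between-subject CV; half-life about 30 h, range 12 to 72 h (4.1); 10% rule (6.3.1).

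**Assumptions not in the documents.** Fed:fasted ratio F of 0.8 or 1.25; within-subject CV 20%; true slope 1; fasted levels 5, 15 and 25 mg, one of them repeated fed; next dose 75 mg, fasted. The doses serve the arithmetic only.

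**Step 1: slope.** Omitting the food factor gives, in expectation,

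slope bias = ln F × cov(fed, ln dose) / var(ln dose), over four equal-sized periods.

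Fed repeat at 25 mg: mean ln dose = 2.689, variance = 0.4318, covariance = (3.219 − 2.689)/4 = 0.1325. For F = 0.8 the bias is −0.2231 × 0.1325/0.4318 = −0.068, so the slope is 0.93.

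**Step 2: exceedance.** Total log SD = √(ln 1.25 + ln 1.04) = √(0.2231 + 0.0392) = 0.512. Set the limit so that the true exceedance is 10%, i.e. 1.2816 × 0.512 = 0.656 above the true log mean. Then:

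- Shift in predicted log mean = (ln F)/4 + slope bias × (ln 75 − mean ln dose) = −0.056 − 0.0685 × 1.629 = −0.167.
- Added residual variance = (ln F)² × (0.1875 − cov²/var) = 0.0498 × 0.1468 = 0.0073, so the SD becomes 0.519.
- Predicted exceedance = 1 − Φ((0.656 + 0.167)/0.519) = 5.6%.

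| Fed repeat at | var | cov | F = 0.8: slope, predicted | F = 1.25: slope, predicted |
|---|---|---|---|---|
| 5 mg | 0.4910 | −0.1693 | 1.08, 14.2% | 0.92, 7.2% |
| 15 mg | 0.3454 | 0.0367 | 0.98, 7.4% | 1.02, 14.2% |
| 25 mg | 0.4318 | 0.1325 | 0.93, 5.6% | 1.07, 17.3% |

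At F = 1 the slope is 1.00 and the prediction is 10.0%. If fasted levels run 5, 15, 25, 50 and 100 mg with 25 mg repeated fed and 200 mg next, the slope stays at 1.00 and the predictions are 9.0% and 11.7%.

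**Step 3: variance alone.** Setting the shift to zero and keeping the larger SD (0.518 to 0.521) gives 1 − Φ(0.656/0.518) to 1 − Φ(0.656/0.521), or 10.3% to 10.4%. For F = 0.5 or 2 it is 12.5% to 13.4%.

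**Step 4: divided doses.** One-compartment superposition of 2 or 3 equal parts 12 or 8 h apart (absorption 1 to 2 per h, half-life 12 to 72 h), relative to the same total given once:

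- Cmax ratio: 0.76 to 0.95 (two parts), 0.69 to 0.94 (three).
- AUC(0-24) ratio: 0.75 to 0.83 (two), 0.67 to 0.76 (three).
- AUC(0-∞) ratio: 1.00 under linear kinetics.

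**Step 5: does the correction work?** In mixed-model simulations with 200 runs per scenario, restricting to fasted profiles gave mean slopes of 0.99 to 1.01 and within-subject SD 0.18 to 0.20 (true 0.198). It drops 6 of 24 active profiles when one period in four is fed. In separate runs with CVs of 40% between and 20% within subjects, a fed term returned the slope to 1.00 and the SD to 0.19 to 0.20.

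Steps 1 to 3 use expected least-squares fits and a lognormal plug-in, one parameter at a time. They approximate the MCMC predictive and ignore parameter uncertainty.

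**The case against.** The strongest reply is that the protocol expects no material food effect (4.4), and with F = 1 food causes no bias. That stands. But the study was designed to test this expectation, and Protocol 4.1.1 limits the dose given with food in case absorption rises, so the model should not depend on it.

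Other safeguards also stand. Protocol 10.3.1 uses the Bayesian probabilities alongside safety and tolerability data, and under Protocol 5.5 one subject above either limit stops escalation. These reduce the consequence for subjects but do not correct the prediction or the final slope. SAP Appendix 8 allows adjustment when model assumptions fail, but that does not say which profiles enter the model.

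A reader might infer more than the documents support:

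- **That the SAP directs pooling on total dose.** It does not. Pooling follows from the default population and the lack of an exclusion; the meaning of dose under division is undefined.
- **That food state is unrecorded.** The food-effect model has a fed/fasted factor and its table shells compare fed with fasted, so the variable must exist. Eight codes also match two cohorts of four periods. What is missing is a label.
- **That inflated variance is the main problem.** Step 3 shows it is small for a 20% to 25% food effect, and it errs towards caution.
- **That dividing a dose halves Cmax.** With a half-life of 12 to 72 h, Step 4 gives a far smaller reduction.
- **That upper doses will be fed or divided.** Both are options only.

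**Conclusion.** The point holds for Part A as a gap in the specification with a calculable, conditional effect. Both power models, applied as written, mix fed with fasted profiles once the planned fed period has been run.

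For fed:fasted ratios of 0.8 or 1.25 under the stated assumptions, the expected slope lies between 0.92 and 1.08, and a true 10% exceedance is predicted at about 5.6% to 17%. The error goes either way. It depends on where the fed dose sits: with a mid-range fed dose the slope stays near 1, although the intercept can still move. It vanishes if food has no effect.

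Division, if used, matters for Cmax and AUC(0-24), and so for the Bayesian model and the Cmax slope. It does not matter for AUC(0-∞) under linear kinetics.

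In Part B each subject receives one dose level, and feeding or division would normally vary by cohort. With at most four cohorts, a regimen effect is then largely confounded with dose.

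**What to change.** **Part A.** In SAP 7.1.2 and 7.2.1.3.2, do one of the following:

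- Add fed/fasted as a fixed effect to both power models, and compute the exceedance probability for the feeding state proposed next.
- Restrict both models to fasted, undivided profiles where these cover the dose range. If later levels are given only with food, the restriction removes those levels and the food term is needed.

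**Definitions.** State what dose and tau mean when a dose is divided. In SAP 10.4.1, give fed and divided periods their own display labels.

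**Part B.** Do not rely on a regimen term. Limit the slope to cohorts on the same regimen, or report it as confounded with regimen.

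**Cost.** One model term, or the loss of about 6 fed profiles, plus a label. The data are already collected. If only the highest Part A doses were divided, a term for division could be separated from dose only by extrapolating the slope, so restricting to undivided profiles is the sounder choice there.
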